In humans, oral bioavailability of metformin does not differ between diabetics and non diabetics, nor between men and women; it is reduced by concomitant assumption of food and it does not proportionally increase as dosage increases (61).

Plasma levels of metformin are mainly influenced by age and eGFR (62–64), than by OCT (Organic Cations Transporter) polymorphisms. In fact, Duong and coll. (63) have demonstrated that, in order to avoid MALA onset, metformin plasma levels have to be lower than 2,5 mg/l, thus it is useful to adapt metformin dosage to eGFR, avoiding to overcome these ratios: 500 mg of metformin if eGFR lower than 15 ml/min, 1,000 mg if eGFR <30 ml/min, 2,000 mg if <60 ml/min, 3,000 mg if <120 ml/min.

Diuretics (65,66), even if able to induce eGFR reduction because of dehydration, are not able "per sè" to reduce metformin clearance, unlike proton pump inhibitors. As they block OCT (67).

Even if metformin is excreted un-modified by the kidney, liver failure can itself reduce metformin excretion, thus increasing metformin toxicity (68).

Metformin effects on glycemic control are directly proportional to basal glucose and insulin levels; in fact in healthy individuals metformin has no influence on fasting glucose levels, but significantly reduces after-meal insulin levels (69).

Metformin activates AMPK (AMP dependent Protein Kinase) in a dose dependent manner, thus causing forced inhibition of mTOR (mammalian Target of Rapamycin) and CFTR (Cystic Fibrosis Transmembrane conductance Regulator).

Very recent published data suggests that the mechanism of action of metformin in vivo may involve pathways other than those related to AMPK. It is critically important to determine whether the potential therapeutic effects of metformin that has been identified in the context of ADPKD are due to its capacity to activate AMPK or are, instead, due to its effects on other targets.

Recent research indicates that metformin can decrease cellular levels of cAMP. This is especially relevant in the setting of ADPKD because a substantial body of research has demonstrated that elevation of cAMP promotes cyst growth in vitro and in vivo. Furthermore, drug therapies that reduce cAMP are able to slow cyst growth both in mouse models of ADPKD as well as in human ADPKD patients (70).

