Once the appropriate essential information has been provided to the subject and fully explained in layman's language by the investigator (or a qualified designee) and it is felt that the subject understands the implications of participating, the IRB/IEC-approved written ICF shall be personally signed and dated by both the subject and the person obtaining consent (investigator or designee), and by any other parties required by the IRB/IEC. The subject shall be given a copy of the signed ICF; the original shall be kept on file by the investigator. All of the above mentioned activities must be completed prior to the subject's participating in the trial. Every phase of the trial will be conducted in compliance with the protocol, GCP and the applicable regulatory requirement.

The trial contemplates a **2 weeks screening period** (included in a 9 months total recruitment period) during which 3 visits have to be collected (the 1st and the 2nd in three days, and the 3rd after biochemical analyses performed during the first two visits have been reviewed). The subject's eligibility for the trial will be confirmed by the mean of eGFR calculated from the 2 pre-treatment, central-lab, serum creatinine assessments. Longer screening periods (up to 4 additional weeks) are acceptable for subjects needing stabilization after changing or discontinuing other treatments, especially anti-hypertensives and diuretics. In this case Subjects must sign ICF and then agree to be switched to an alternate form of therapy in order to be eligible. As part of this stabilization or wash-out period different lab safety tests may be performed. Subjects who fail to meet trial requirements during the screening period may be rescreened at a later date.

Once eligibility is assessed, patients will undergo non-contrast enhanced CT-scan of kidneys (if not performed within six months prior to randomization).

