5.2 Inclusion Criteria

- 1) Men and women aged between 18 and 50 years
- 2) eGFR (CKD-EPI) ≥ 45 ml/min/1,73 m2
- 3) Genetic Diagnosis of Type I ADPKD truncating mutation
- 4) Signed and dated informed consent

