6. TREATMENT

6.1 Treatment dose and schedule

Subjects will be instructed to take the following doses for titration:

- 1 tablet 45 mg upon waking and 1 tablet 15 mg approximately 8 to 9 hours later for 1 week;
- 1 tablet 45 mg + 1 tablet 15 mg upon waking and 2 tablets 15 mg approximately 8 to 9 hours later for 1 week;
- 2 tablets 45 mg upon waking and 2 tablets 15 mg approximately 8 to 9 hours later for 1 week.

During run-in period, subjects will take the maximum dose of tolvaptan achieved during titration (or at least 45/15 mg).

For the Metformin titration period and subsequent run-in period, subjects will receive 2 packages at the first visit of metformin 500 mg.

Subjects will be instructed to take the following doses for titration:

- 1 tablet 500 mg upon waking for 1 week;
- 1 tablet 500 mg upon waking and 1 tablet 500 mg approximately 8 to 9 hours later for 1 week;

1 tablet 500 mg upon waking, 1 tablet 500 mg approximately 8 to 9 hours later and 1 tablet
 500 mg approximately 8 to 9 hours later for 1 week.

During run-in period, subjects will take the maximum dose of metformin achieved during titration (or at least 500/500 mg).

If the subject cannot tolerate the lowest permitted doses, he/she will be deemed a titration failure or a run-in failure.

During the on-treatment period, the patient will take the maximum tolerated dose achieved during titration and run-in. The subject will stay on that dose for the entire trial, if not otherwise contraindicated by AEs or not tolerated.

Patients on metformin experiencing eGFR reduction below 45 ml/min, can not take more than 1000 mg a day of metformin (thus reducing from 1500 mg a day to 1000 mg a day).

Those patients on Jinarc will receive 1 package containing 4 blisters (irrespectively of the dosage).

Those patients on Zuglimet will receive 2 packages (all containing 3 blisters of 10 tablets) if on 500/500 mg a day, 3 packages if on 500/500/500 mg a day.

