9.1.6 Efficacy Assessments

9.1.6.1 Serum Creatinine for Estimated Glomerular Filtration Rate

The serum creatinine concentration is related to eGFR and is commonly used to estimate renal function in clinical practice. Alteration in metabolism of creatinine and methodological interference in its measurements may impact accuracy of the serum creatinine and renal function estimation. Below are suggested measures to decrease serum creatinine variability prior to the monthly blood draws required by this protocol:

- Maintain a stable dietary protein intake and avoid very different or high cooked meat protein meals the day before each scheduled serum creatinine assessment;
- Maintain a stable exercise routine and avoid very different or heavy physical activity/exercise the day before each scheduled serum creatinine assessment;

- Maintain a stable water intake, aimed at avoiding thirst consistently throughout the trial recommended ingestion of at least 2-3 liters of fluid (including in solid, semi-solid, and liquid foods) per day, unless otherwise directed by your study doctor;
- Plan to arrive at the same time for each blood-draw and clinic visit to better standardize time of the sample collection throughout the trial;
- Avoid forbidden medications.

Serum creatinine is stable when stored frozen; therefore, blood sample will be analyzed by the laboratory as soon as it is received and accessioned.

Ongoing, analysis will be conducted for each subject upon his/her individual completion of all their assessments within the trial (not at the end of the trial).

The eGFR values will be calculated from the laboratory serum creatinine concentrations taken at screening and during every trial visit. In the screening period, the first two assessments must be used to determine the eGFR values that will be averaged for determination of meeting inclusion criteria.

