15. FIGURES AND TABLES

FIGURE 1

	SV1	SV2	EoTI	EoRI	M3	M6	M9	M12	M15	M18	M21	M24	FU1	FU2
EXAMS A	Х	Х		Х	Х	Х	Х	Х	Х	Х	Х	Х	Х	Х
EXAMS B	х				I 1									
EXAMS C	х			х	х	х	х	х	х	х	х	х	х	х
EXAMS D	х				х	х	х	х	х	х	х	Х		
EXAMS E	х			Х	х	х	х	Х	х	х	х	Х		Х
EXAMS F	х				х	х		х		х		Х		Х
EXAMS G	х				I 1			х				Х		
PHYSICAL EXAMINATION	х	Х		Х	х	х	Х	Х	х	х	Х	Х	х	Х
ARTERIAL BLOOD PRESSURE	х	Х		Х	х	х	Х	Х	х	х	Х	Х	х	Х
POST VOID BODY WEIGHT	х	Х		Х	х	х	Х	Х	х	х	х	Х	х	Х
HEIGHT	х				1									
KIDNEY CT SCAN (non contrast)		Х										Х		

SCREENING PERIOD (2 WEEKS) SV 1 = SCREENING VISIT 1 SV 2 = SCREENING VISIT 1 KIDNEY CT SCAN IMP TITRATION PERIOD (DAY -28, DAY -8) EOTI = END OF TITRATION IMP RUN-IN PERIOD (DAY -7, DAY -1) EORI = END OF RUN-IN ON-TREATMENT PERIOD (24 MONTHS) M = MONTH FOLLOW-UP PERIOD (3 WEEKS) FU1 = FOLLOW UP VISIT 1 (DAY +8) FU2 = FOLLOW UP VISIT 2 (DAY +21)

FIGURE 1 (LEGEND EXAMS)
EXAMS A
CREATININEMIA
EXAMS B
PT INR
EXAMS C
AST
ALT
BILIRUBIN TOT+FRACTIONED
UREA
URATE
PHOSPHATE
GLYCEMIA
VENOUS BLOOD GAS ANALYSIS
EXAMS D
GLYCOSYLATED HAEMOGLOBIN
EXAMS E
SERUM B-HCG
EXAMS F
COMPLETE BLOOD COUNT
SERUM CYANOCOBALAMI
EXAMS G
uPCR*
uACR*
uMCP-1*
uEGF*
INSULINEMIA*
KIDNEY CT SCAN

[figure not shown]

FIGURE 2

FIGURE 3

RECRUITMENT(9 M)							
SCREENING (2W	V)	ADDITIONAL SCREENING (8W)					
RANDOMIZATION							
TREATMENT (4W+24 M)							
TITRATION (3W)	RUN-II	N (1W)	MANTENIMENTO (24 M)				
END OF TREATMENT							
FOLLOW-UP (3W)							
VISIT 1		VISIT2 2					

FIGURE 4

[figure not shown]

TABLE 1						
Boceprevir	Clrithromycin	Clotrimazole	Indinavir			
Itraconazole	Ketoconazole	Lopinavir	Mibefradil			
Nefazodone	Nelfinavir	Posaconazole	Ritonavir			
Saquinavir Telepravir		Telithromycin	Voriconazole			

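### Section 9.1.6.1 ties eligibility to the first two screening creatinines even when screening is extended for a medication change, so a patient near eGFR 45 can be judged on a regimen no longer followed

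*Combined protocol and SAP*

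**What the plan says.** Section 5.2 requires "eGFR (CKD-EPI) ≥ 45 ml/min/1,73 m2". Section 4 says that eligibility is "confirmed by the mean of eGFR calculated from the 2 pre-treatment, central-lab, serum creatinine assessments", and Section 4.1 adds that the two draws are at least 24 hours apart. Section 9.1.6.1 is stricter: "In the screening period, the first two assessments must be used to determine the eGFR values that will be averaged" to decide whether the inclusion criterion is met.

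Section 4 also provides: "Longer screening periods (up to 4 additional weeks) are acceptable for subjects needing stabilization after changing or discontinuing other treatments, especially anti-hypertensives and diuretics". Section 4.1 and Figure 3 give the extension as up to 8 weeks, not 4. On testing in that interval, Section 4 says only: "As part of this stabilization or wash-out period different lab safety tests may be performed". No section asks for an eligibility creatinine after stabilisation.

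The protocol accepts that these drugs matter. Section 2.2.3 describes diuretics as "even if able to induce eGFR reduction because of dehydration", Section 5.3 excludes patients taking them, and Section 6.3 lists RAAS blockade among treatments that alter creatinine.

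**The concern.** The extension exists so that a patient can settle on a new regimen before entering the trial. If the two eligibility draws have already been taken, the criterion is applied to a value from the old regimen, in the very patients for whom the extension was written.

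Two errors are possible. A patient whose stabilised eGFR is adequate may be rejected. A patient whose stabilised eGFR is below 45 may be randomised and enter titration. If the same two values also serve as the eGFR baseline, the regimen change would appear as an early step in that patient's slope.

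**Working it through.** The plan gives no figure to reproduce: it states no size for the shift and no number of patients with extended screening. The check is mainly a comparison of sections.

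**1. Do the draws come before the switch?**
- Section 4: visits 1 and 2 fall within three days, and visit 3 follows review of their results.
- Section 9.1.1: blood is taken at visits 1 and 2 only.
- Sections 4 and 6.3: consent comes before the switch.
- Figure 1: SV1 and SV2 belong to the 2-week screening period. Figure 3 lists the additional screening after that period.

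The natural reading is draws first, extension second. No sentence requires that order.

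**2. Would a wrongly admitted patient be noticed before titration?**
- Section 4 calls for screening points 2 to 8 at Day -29 and Day -1. Point 8 includes serum creatinine.
- Section 9.1.2 lists the randomisation assessments and includes no blood sample. In Figure 1 the next creatinine after SV2 is at the end of run-in.
- Section 9.1.2 does require the inclusion criteria to be verified, but under 9.1.6.1 that check still uses the first two values.

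On Section 9.1.2 and Figure 1, the first scheduled creatinine after the switch can be Day -1. The up-titration steps in Section 4.3 are on Day -22 and Day -15. Section 6.1 says: "Patients on metformin experiencing eGFR reduction below 45 ml/min, can not take more than 1000 mg a day of metformin". That provision operates only once a value below 45 has been measured.

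**3. Who changes status?** Let x be the assumed relative error in the screening eGFR compared with the stabilised value.
- Screening reads low: stabilised values from 45 to 45/(1 - x) are rejected.
- Screening reads high: stabilised values from 45/(1 + x) to 45 are admitted.

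| Assumed x | Wrongly rejected | Wrongly admitted |
|---|---|---|
| 3% | 45 to 46.4 | 43.7 to 45 |
| 5% | 45 to 47.4 | 42.9 to 45 |
| 10% | 45 to 50.0 | 40.9 to 45 |

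For stopping a diuretic, Section 2.2.3 points to a low reading, hence wrongful rejection. Wrongful admission needs a change that lowers eGFR. Section 6.3 says that RAAS blockade alters creatinine but gives no direction.

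**4. Effect on the slope, if these two values are the baseline.** At eGFR 50, a shift of 3% to 10% is a step of 1.5 to 5 ml/min/1.73 m². Assume an averaged baseline 10 weeks before Day 0, then values at Day -1 and at eight three-monthly visits, with 28-day months.
- Least-squares slope: a unit step after baseline contributes 0.233 per year, so 1.5 to 5 gives 0.35 to 1.2 ml/min/1.73 m² per year in an affected patient.
- Baseline to Month 24 only: the interval is 70 + 672 = 742 days, or 2.03 years. The factor is 1/2.03 = 0.49, giving 0.7 to 2.5.
- Placing the baseline 5 to 14 weeks before Day 0 moves these factors only to 0.22–0.24 and 0.47–0.52.

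The medication change precedes randomisation, so affected patients are balanced between arms on average. If 10% are affected (assumed) with 75 per arm, the SD of the difference in affected proportions is sqrt(2 × 0.1 × 0.9/75) = 0.049. Multiplied by 0.35 to 2.5, this is a chance shift in the arm difference with an SD of about 0.02 to 0.12. For scale, 10% of the annual declines of 2.72 and 3.70 quoted in Section 12.1 is 0.27 and 0.37.

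**The case against.** The strongest reply is that the order of events is inferred. Only consent must precede the switch, so a site could obtain consent, complete the wash-out, then draw both samples, and comply fully with 9.1.6.1. Figure 3 is a layout of periods, not a blood-draw schedule. This stands. A reader might infer that every extended-screening patient is judged on pre-switch values, and the documents do not support that. What remains is that the text permits it, the described workflow points that way, and sites may differ.

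A second reply is that nothing is really discarded. Figure 1 schedules only two screening creatinines, so the first two may simply mean SV1 and SV2, and the wash-out tests are optional safety tests. That is a fair reading, but it confirms that no post-stabilisation value is required. Fixing the pair in advance also stops repeat testing until a patient qualifies. That merit is real, and the fix should keep it.

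Third, Sections 4 and 11 allow screen failures to be rescreened, with all screening procedures repeated unless consent was withdrawn. This largely answers wrongful rejection, provided the new pair is drawn on the new regimen. It does nothing for wrongful admission. There, the criteria check at randomisation and the Day -1 bloods are only partial safeguards: the first relies on the same average, and the second comes after titration.

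**Conclusion.** The point holds as a gap in the eligibility rule. Followed as written, 9.1.6.1 can apply the threshold of 45 to values from a regimen the patient has left, and no section clearly catches a wrongful admission before titration. It concerns only patients whose screening is extended for a medication change and whose eGFR lies near 45. Their number is unknown. The 3% to 10% shift and the 10% prevalence are illustrations, not figures from the documents.

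A reader might also infer that the rule biases the primary comparison. The documents do not support that. The sentence in 9.1.6.1 concerns inclusion only, and Section 8.1.1 speaks merely of an appropriate baseline, so use of these two values in the slope is conditional. Even then the step arises before randomisation and adds chance imbalance, not a systematic difference between arms. The case for changing the text is that the error is avoidable at almost no cost, not that it threatens the trial's main result.

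**What to change.** Amend 9.1.6.1 to say that, where screening is extended for a medication change, the two eligibility creatinines (central laboratory, at least 24 hours apart) are the first two taken after stabilisation and before randomisation. Patients without an extension continue to use SV1 and SV2. State that any pre-randomisation eGFR baseline uses the same two values. Specifying the first two after stabilisation, not the last two before randomisation, avoids picking up a Day -29 draw and prevents repeat testing from altering eligibility.

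Also reconcile:
- the extension length: 4 weeks in Section 4, against 8 weeks in Section 4.1 and Figure 3;
- blood sampling at randomisation: required in Section 4, absent from Section 9.1.2 and Figure 1.

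The sponsor should confirm that Sections 4.3 and 6.1 work together for a patient found below 45 around titration. This review proposes no dosing rule.

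The cost is at most one extra pair of creatinines in extended-screening patients, and none where a site already draws after the wash-out.

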9.1.6.2 TKV measurement

Abdomen-pelvis CT-scan will be performed by using a 320-row multi detector device and the following acquisition parameters will be used: slice thickness 0.5 mm, increment 0.5 mm, rotation time 0.5 s; 120/200 kVp/mAs.

An automatic dose modulation system will be used in all cases. Images will be acquired without intravenous injection of iodinate contrast material. Scans will be performed from the diaphragm to the pubic symphysis.

CT data will be centrally transferred to and analysed on a workstation (HPXW8600), present within the DETO equipped with software dedicated to image reconstruction (Vitrea FX 2.1, Vital Images, Minneapolis, MN, USA). For each patient, Multi-planar Reconstructions (MPR) on the axial, coronal and sagittal planes and Volume Rendering

(VR) images will be used in order to assess renal parenchyma. A radiologist with more than 10-year experience in the field of abdominal CT will manually trace both kidneys (renal parenchyma and all cysts including exophytic cysts), excluding the renal pelvis and other hilar vascular structures. The semi-automatic 3D Analysis software will be used in order to quantify the TKV for each CT examination. All changes in TKV (delta TKV) will be calculated by analyzing any variation of absolute TKV values deriving from the different CT examinations.

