1. SYNOPSIS	
TITLE	Metformin versus Tolvaptan in adults with Autosomal Dominant Polycystic Kidney Disease (ADPKD): a phase 3a, independent, multi-centre, 2 parallel arms randomized controlled trial
SPONSOR	Università degli Studi di Bari Dipartimento dell'Emergenza e dei Trapianti di organi (D.E.T.O.)
PHASE	III
RATIONALE	Autosomal dominant polycystic kidney disease (ADPKD) is the most common inherited renal disorder occurring in 1:400–1:1.000 live births. It affects 4 to 6 million persons worldwide and about 205.000 people in Europe (EU). This figure is equivalent to 4 in 10.000 people and thus below the prevalence threshold of 5 in 10.000 used to designate a disease as rare in EU. Renal cyst development and expansion in ADPKD involves both fluid secretion and abnormal proliferation of cyst-lining epithelial cells. The chloride channel of the cystic fibrosis transmembrane conductance regulator (CFTR) participates in secretion of cyst fluid, and the mammalian target of rapamycin (mTOR) pathway may drive proliferation of cyst epithelial cells. CFTR and mTOR are both negatively regulated by AMP-activated protein kinase (AMPK). Metformin, a drug widely used, is a pharmacological activator of AMPK. We found that metformin stimulates AMPK, resulting in inhibition of both CFTR and the mTOR pathways. Metformin induces significant arrest of cystic growth in both in vitro and ex vivo models of renal cystogenesis. In addition, metformin administration produces a significant decrease in the cystic index in two mouse models of ADPKD. These results suggest a possible role for AMPK activation in slowing renal cystogenesis as well as the potential for therapeutic application of metformin in the context of ADPKD
OBJECTIVES	Objective of the study is to assess if a two-year course of 1500 mg oral metformin is effective and safe in treatment of ADPKD, as compared to the actual gold-standard therapy, tolvaptan (Jinarc®)
ENDPOINTS	 Primary outcome of the study is to evaluate the difference between Metformin and Tolvaptan in annualized slope of eGFR (CKD-EPI) for individual subjects, that will be calculated using an appropriate baseline and post-randomization assessment. The key secondary endpoint is the percent change from baseline in htTKV as measured by CT-scan at 24 months. The safety endpoin include: changes from baseline in creatinine; vital signs; laboratory values including liver function tests, rate

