4.2 Randomization visit (Day -30)

Randomization process will be carried out by a WEB-based, internet-accessible, system (e-trial platform). Investigators willing to include a patient should log-in into the e-trial platform and complete the registration form.

The patient allocation number and the treatment arm will be immediately TRASMITTED on line without blinding.

Any controversial eligibility assessment will be discussed with the Study Chair.

Each patient will be informed via a cover letter including clear instructions on participation, drug use, dosing and prescription.

Randomization visit may coincide with CT-scan visit.

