8.1.2 Secondary Endpoints

The key secondary endpoint is *the percent change from baseline in htTKV as measured by CT-scan at 24 months*. The use of htTKV as a surrogate biomarker for progression of ADPKD is supported by the Consortium for Radiologic Imaging Study of Polycystic Kidney Disease (CRISP) which showed that baseline TKV strongly predicts subsequent loss of GFR. TKV is now widely used in RCTs for ADPKD.

Other secondary efficacy end-points include:

- Difference in rate of albuminuria change;

- Difference in rate of urological events and of hypertension onset (for not hypertensive patients at baseline);
- Hypertension worsening or amelioration (for those who are hypertensive);
- Exploratory efficacy Outcomes (changes from baseline in urinary EGF and EGF/MCP-1 levels).

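### No passage specifies that the radiologist who traces kidney volumes by hand is masked to treatment arm, so the Month 24 readings for the key secondary endpoint are unprotected in an open-label trial

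*Combined protocol and SAP*

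**What the plan says.** Section 8.1.2 names as key secondary endpoint "the percent change from baseline in htTKV as measured by CT-scan at 24 months".

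Section 9.1.6.2 describes the measurement. Scans come to one place: "CT data will be centrally transferred to and analysed on a workstation (HPXW8600), present within the DETO". The Synopsis gives the DETO as the sponsor's department. There, "A radiologist with more than 10-year experience in the field of abdominal CT will manually trace both kidneys", and then "The semi-automatic 3D Analysis software will be used in order to quantify the TKV for each CT examination". The section also fixes the acquisition settings and says which structures are counted: all cysts, exophytic ones included, are in; the renal pelvis and hilar vessels are out.

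Allocation is open. Under section 4.2, when an investigator registers a patient, "The patient allocation number and the treatment arm will be immediately TRASMITTED on line without blinding".

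Section 9.1.6.2 says nothing on whether the reader is masked to arm, identity, date or scan order. Section 4.8, on minimising bias, deals with tolerability before entry to the treatment period, reminders of commitment, web randomisation and the cover letter. Section 12.3 does not mention masked assessment.

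**The concern.** In an open-label trial, masked reading of an imaging endpoint is the usual way to keep at least one efficacy result independent of knowledge of treatment. Here the volume depends on a contour drawn by a person, and the plan does not require that person to be unaware of the arm.

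If the reader knows the arm, a small unconscious difference in where the contour is placed on the Month 24 scan adds directly to the difference between arms. It does not shrink as more patients are recruited. Randomisation does not remove it, because it arises after randomisation. The mixed model in section 12.3 cannot separate it from a treatment effect.

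The endpoint matters to this trial: section 3.2 makes slowing of kidney volume growth the main secondary objective, and section 3.1 says precise volume measurement is needed to judge treatment over short periods.

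**Working it through.** The plan gives no power, standard deviation, reader error or reader agreement for kidney volume, so there is no figure of its own to reproduce. The check has four steps.

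**1. Is masking specified anywhere?** I read sections 4.1, 4.2, 4.8, 8.1.2, 9.1.1, 9.1.4, 9.1.6.2 and 12.3 and Figure 1 for any provision on the reader. None is given. There is also no second reader, repeat reading or agreement check.

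**2. Which knowledge biases the comparison?** Suppose the reader adds a shift s to every Month 24 volume because the scan is known to be the later one, and a further shift b only in one arm because the arm is known. Then

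observed difference between arms = true difference + (s + b) − s = true difference + b.

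The common shift s cancels, or largely so if it varies with kidney size. Knowledge of arm is therefore the main threat, and knowledge of date alone is minor.

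**3. How large is a shift relative to expected growth?** Inputs:
- growth of 5–6% per year (section 3.1)
- months of 28 days (section 4.5), so Day 0 to Month 24 is 24 × 28 = 672 days
- baseline scan on Day -30 (section 4.1), so the interval is 672 + 30 = 702 days

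Growth = (1 + g)^(702/365.25) − 1, with 702/365.25 = 1.922 years:
- g = 5%: 1.05^1.922 − 1 = 9.8%
- g = 6%: 1.06^1.922 − 1 = 11.9%

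An assumed arm-related shift of 1 percentage point of baseline volume is then 1/9.8 = 10.2% down to 1/11.9 = 8.4% of total growth. A shift of 2 points is 20.4% down to 16.8%.

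A baseline scan up to six months old is accepted. At that limit the interval is about 702 + 183 = 885 days (2.423 years), growth is 12.6–15.2%, and 1 point is 7.9–6.6% of it.

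**4. What could it do to the test?** This step rests wholly on assumed values: 75 per arm (150 at 1:1, all scanned), a two-sided 5% test, no true difference, and an SD of percent change of 6 to 12 points.

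SE = SD × √(2/75); false-positive rate = Φ(−1.96 + b/SE) + Φ(−1.96 − b/SE).

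| Assumed SD (points) | SE | b = 1 point | b = 2 points |
|---|---|---|---|
| 6 | 0.98 | 17.5% | 53.2% |
| 8 | 1.31 | 11.9% | 33.4% |
| 10 | 1.63 | 9.4% | 23.2% |
| 12 | 1.96 | 8.0% | 17.5% |

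With b = 0 the rate is 5%. The table shows how a shift would act; it is not an estimate for this trial.

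**The case against.** The strongest reply is that silence is not an unmasked reading. That stands. A reader might infer from the words "TRASMITTED on line without blinding" that the radiologist receives the arm. Section 4.2 describes what the platform sends on registration of a patient, and nothing there sends the allocation to the radiologist. Central transfer also separates the reader from the other sites. A baseline scan acquired and traced before randomisation cannot reflect the arm. But no reading time is set, and none of this protects the Month 24 scan.

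Second, a reader might infer that exophytic cysts, the renal pelvis and hilar vessels are left to taste. They are not: section 9.1.6.2 gives a rule for each, with thin slices and semi-automatic quantification. What remains is judgement at the edge of the contour, which is smaller but still made by hand.

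Third, masking to date might seem as important as masking to arm. Step 2 of the working shows that it is not. Nor can it always be achieved: sections 4.1 and 9.1.1 accept an MRI baseline, which reveals its own time point.

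Fourth, a reader might infer a motive from the place of reading. The documents show only that the DETO is the sponsor's department, which is a reason for a safeguard and not evidence of partiality.

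Fifth, the growth rate is a general adult average, whereas this trial enrols patients with truncating mutations, chosen because they are more likely to progress, and treats all of them. This stands as a limit on the illustration.

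**Conclusion.** The point holds in a limited form. Masking of the kidney-volume reader to arm is not specified, and section 9.1.6.2 can be followed exactly while the reader knows the arm. The Month 24 tracings behind the key secondary endpoint are then open to arm-related bias. This is worth correcting but does not threaten the trial's main result, because the primary endpoint is calculated from laboratory creatinine.

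On size, an assumed 1-point shift would be roughly a tenth of expected growth or slightly less (8.4–10.2% with a Day -30 baseline). That rests on the protocol's 5–6% per year and on an assumed shift. The documents do not support a claim that such a shift will occur, how large it would be, or that readings are in fact unmasked.

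**What to change.** Add to section 9.1.6.2:
- At the existing central transfer, scans are stripped of identifiers and of any indication of arm, and given a random code.
- The same reader traces both scans of a patient, masked to arm and, where both scans are CT, also to date and order.
- Tracings are locked before they are linked to allocation.

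This needs no extra scan, visit, patient or reader, and no sample size or significance level changes. It is not without cost, and the documents give no resources from which to price it. Someone other than the reader must keep the code list. To mask order, baseline tracings must be held until the Month 24 scan arrives, or repeated then. Where the baseline is MRI, time point cannot be masked, but arm still can. Masking does not reduce random tracing error, and it does not resolve any mismatch between an MRI baseline and a CT at Month 24.

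If the reader is already masked in practice, the change is a sentence recording it. If not, it should be in place before Month 24 reading starts, since unmasked tracings would have to be redone.
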